1. SUMMARY

Study Title	“Pre-implantation genetic testing for monogenic disease: single center experience.”		
Study code	GIN2/OSS_001/2023	Acronym:	PGT-M experience
Version and Date	Version No.1 (29/06/2023)		
Sponsor (Institution)	Humanitas Research Hospital, [name]		
Coordinating Investigator	[name] [name]		
Product Name	NA		
Study indication	Efficacy of pre-implantation genetic testing for monogenic diseases in a single center scenario.		
Background and rationale	
From the early 1990s, preimplantation genetic diagnosis (PGD) and embryo biopsy became available: over the years, with the evolution of the technique, PGT-M has revolutionized the landscape of clinical genetics by decreasing the risk of transmitting a serious genetic disorder to patients offspring and allowing to potentially eliminate the disease from the population. With the term PGD, we include three different tests: pre-implantation genetic testing for monogenic disease (PGT-M), Pre-implantation genetic testing for aneuploidy (GT-A), and Pre-implantation for structural rearrangements (PGT-SR). PGT-M is used in patients who have or are carriers of a congenital disease that can be passed down to their offspring. Pre-implantation genetic testing for aneuploidy (PGT-A) is a procedure that screens embryos before transfer to reduce the risk of aneuploidy and chromosomal abnormalities. Pre-implantation for structural rearrangements (PGT-SR) is an option for patients with an inversion, reciprocal translocation, or Robertsonian translocation.
 
These approaches, when combined with in vitro fertilization (IVF), enable us to differentiate between affected and unaffected embryos. To achieve these biopsy results, many IVF laboratories perform trophectoderm cell biopsies (TE), which is the development of embryos up to the blastocyst stage, which occurs 5-7 days after fertilization. Prior to trophectoderm cell biopsies (TE), biopsies were performed on polar bodies or cleavage embryos.
		

	
It is still open to debate the disadvantage discussed in the scientific literature that affects the technique's efficacy due to the presence of mosaic embryos and whether it should be paired with PGT for aneuploidy (PGT-A) for more concrete results.


Study Objectives
	
The primary objective of this retrospective observational single-center study is to describe the efficacy of PGT-M in a real-life setting. Efficacy will be evaluated in terms of live birth rate (LBR), simple and cumulative live birth rate (CLBR) per couple, and abortion rate (AR). Furthermore, investigators will consider how many cycles the participants need to undergo to achieve a viable blastocyst.
 
The secondary objective is to evaluate the incidence of aneuploidy in tested embryos, in order to understand the need for PGTA in addition to PGTM.

Study Endpoints/Outcomes
	
For the evaluation of the study objectives, all patients that underwent PGTM from 2016 to 2022 will be included in the study.
 
The results obtained from the PGT-M will be calculated as:
 
Live birth rate (LBR): defined as the “the number of deliveries that resulted in at least one live birth, divided by the number of cycles.” Embryology and Alpha Scientists in Reproductive Medicine. Electronic address [1]
 
Cumulative live birth (CLBR) per couple: defined as the “delivery of at least one live-born infant (>24 weeks of gestation) in the fresh or in the subsequent frozen-thawed cycles in relation to the number of oocytes retrieved per couple.” Polyzos, Drakopoulos [2]
 
Abortion rate (AR): is defined as the “spontaneous demise of a pregnancy before the foetus reaches viability. The term therefore includes all pregnancy losses (PLs) from the time of conception until 24 weeks of gestation.” Group, Vlaisavljevic [3]
 
Aneuploid embryo rate: “the most common genetic abnormality

	resulting in embryonic demise, pregnancy loss, and congenital birth defects. At the preimplantation stage, ~50% of the IVF-derived embryos have chromosomal abnormalities that are incompatible with implantation or normal fetal development.” Hindi E. Stohl [4]
Study design	Monocentric retrospective observational study
Product/Intervention	PGT-M is an option for all patients, fertile and infertile, who are at risk of transmitting a monogenic disease to their offspring. PGT-A is only performed on unaffected embryos that have undergone PGT-M; therefore, investigators do not know the percentage of aneuploidy in affected embryos.
Eligibility Criteria	Patients fertile or infertile that have undergone preimplantation genetic testing for monogenic diseases (PGTM). No exclusion criteria will be considered.
Study Procedures	The information collected for the database will be retrieved from the Fertility Center internal web-based registry where data about pregnancy follow up are noted. The study database includes all PGTM cycles performed between 2016-2022 at the Humanitas Fertility Center.
Number of patients (planned)	All 76 patients who underwent PGTM testing in the Fertility Center starting from the beginning of 2016 and going through the end of 2022 will be included in the study.
Investigational Sites (planned)	University affiliated 3 rd level Fertility Center
Sample size and statistical consideration	Data will be described as number and percentage, if categorical, or mean and standard deviation, if continuous and approximately Gaussian, or with median and range.
Study timetable	
 7 years of inclusion

GCP Statement:	This study will be conducted in compliance with the protocol, the current version of the Declaration of Helsinki and applicable guidelines as well as all national legal and regulatory requirements.
-----------------------	---

2. STUDY FLOW-CHART

Procedures	Blastocysts trophectoderm biopsy
PGTM analysis	567 embryos

3. BACKGROUND

Handyside et al. were the first to publish research on pre-implantation genetic testing for cystic fibrosis in 1992. The study aimed to take cells from a cleavage-stage embryo and use DNA amplification to look for the cystic fibrosis mutation. A total of 13 embryos were biopsied from the three patients. Only one of the four suitable for transfer resulted in a pregnancy and the subsequent birth of a healthy baby. According to the study, couples have a high chance that their pregnancy will be unaffected by cystic fibrosis. As a result, pre-implantation diagnosis was considered clinically accurate, despite it taking several years to confirm its accuracy.[5]

A 2005 study published by **McArthur et al.** aimed to compare trophectoderm biopsies with their previously published experience with day-3 cleavage-stage embryos. They found that blastocysts have a lower percentage of chromosomal monosomies than cleavage-stage embryos. Meanwhile, performing a biopsy in the cleavage stage can arrest further development by reducing the inner cell mass, which is not the case for trophectoderm biopsies. Concluding that trophectoderm biopsies are a practical addition to IVF and great progress for PGD practices. [6]

A review done by **Harper et al.** in 2017 explained the advantages and disadvantages of the different biopsy methods for pre-implantation genetic screening (PGS) and pre-implantation genetic diagnosis (PGD). Three stages are available for biopsy: polar bodies from oocytes, blastomeres from cleavage-stage embryos, and trophectoderm cells from blastocysts. The polar body is the earliest stage that can be biopsied but is limited by the fact that only maternal errors can be tested. The second stage is cleavage embryos, which until recently lost their popularity since these cells are more mosaic and the number of cells biopsied is limited. The majority of pre-implantation is now done at the blastocyst stage, which is already a method of selection as only good-quality embryos reach the blastocyst stage. The advantages of a trophectoderm biopsy are that the cells are less mosaic and more abundant to analyze, making the results more accurate. This review agrees with the outcomes of the study above: that trophectoderm biopsies are the best technique for pre-implantation genetic testing.[7]

In 2018, a study done by **Zanetti et al.** described the cases of PGT-M in fertile couples in a Brazilian IVF center and compared their results to those reported by the European Society of Human Reproduction and Embryology (ESHRE) Consortium PGD XIV–XV. They mentioned the prevalence of trophectoderm biopsies and how they have become a highly viable option due to the excellent survival rates in embryo culture. They obtained a 22.1% implantation rate, a 26.8% pregnancy rate, and a 7.1% miscarriage rate. These results were comparable with ESHRE consortium cycles. They conclude that PGT-M is a very feasible option for families affected by monogenic disease. [8]

Goldman et al. published a study in 2016 with the goal of understanding the benefits of concurrent testing for both monogenic disorders and aneuploidy in a population of patients undergoing blastocyst culture, trophoctoderm biopsy, and single gene testing, with and without aneuploidy screening. There are two goals: first, to quantify the incidence of aneuploidy in a population of patients undergoing trophoctoderm biopsy and PGD for a single gene disorder, to better understand the benefits of dual-testing and the potential risk of not performing concomitant aneuploidy screening, and second, to determine the risk of not performing concomitant aneuploidy screening. Most patients (53.2%) had at least one blastocyst that was unaffected by monogenic disease but were affected by aneuploidy. Without screening, these unaffected but aneuploid embryos would have been transferred, leading to implantation failure, pregnancy loss, or a pregnancy affected by chromosomal aneuploidy. Therefore, the obstetrical outcomes, such as the live birth rate, were higher and the abortion rate was lower for those who underwent concomitant aneuploidy screening. When performed together with PGD, aneuploidy screening offers useful information for selecting embryos and significantly improves the rate of single embryo transfer. This study concluded that a significant increase in single embryo transfer rates between the dual-screening group and the monogenic disease-tested group shows that concurrent screening significantly benefits embryo selection. [9]

A retrospective case-control study done by **Shen et al.** had the objective of determining the application value of next-generation sequencing (NGS)-based pre-implantation genetic testing for aneuploidies (PGT-A). They performed NGS-based aneuploidy screening on multiple displacement amplification (MDA) products of embryonic trophoctoderm biopsy samples that were frozen after PGT-M with known transfer outcomes. A total of 76 embryos, which resulted in live birth after transfer, showed that if the patients had PGT-A during their PGT-M cycle, 17.1% of the embryos would have been wasted due to being diagnosed as affected. It can then be understood that Shen et al. along with their data, believe that PGT-A might cause more harm than benefit for patients undergoing IVF. [10]

In a review published in 2022, **Scriven et al.** explored the potential harmful effect of combining PGT-M with PGT-A. The most recent ESHRE PGT Consortium data were incorporated. Combining testing for unrelated sporadic chromosomal abnormalities (PGT-A) and excluding embryos with chromosomally abnormal results from transfer offers the opportunity to reduce the risk of miscarriage and the number of embryo transfers, but it also risks excluding healthy embryos from transfer due to abnormal test results that do not reflect the embryo's true potential. The data was divided into two categories in the review: high-success clinics and typical-success clinics. The clinic success groups are subjective and are based on the number of live births per embryo transplanted (high success is 60% PGT-MA vs. 50% PGT-M) and typical success is 45.6% PGT-MA (38.0% compared. PGT-M). Both success groups had identical miscarriage rates per clinical pregnancy. The PGT-MA live birth rate per embryo transplanted is higher (45.6% vs. 38.0%), demonstrating that testing for unrelated chromosomal gain or loss can help determine if an embryo is viable. All scenarios reveal that PGT-A reduces the chance of miscarriage just slightly at the expense of healthy live births. This study concludes that PGT-M without PGT-A is preferable for achieving an undamaged live birth. [11]

3. Rationale

From the early 1990s, preimplantation genetic diagnosis (PGD) and embryo biopsy became available: over the years, with the evolution of the technique, PGT-M has revolutionized the landscape of clinical genetics by decreasing the risk of transmitting a serious genetic disorder to patients offspring and allowing to potentially eliminate the disease from the population. With the term PGD we include three different tests: pre-implantation genetic testing for monogenic disease (PGT-M), Pre-implantation genetic testing for aneuploidy (PGT-A) and Pre-implantation for structural rearrangements (PGT-SR). PGT-M is used in patients who have or are carriers of a congenital disease that can be passed down to their offspring. Pre-implantation genetic testing for aneuploidy (PGT-A) is a procedure that screens embryos before transfer to reduce the risk of aneuploidy and chromosomal abnormalities. Pre-implantation for structural rearrangements (PGT-SR) is an option for patients with an inversion, reciprocal translocation, or Robertsonian translocation.

These approaches, when combined with in vitro fertilization (IVF), enable us to differentiate between affected and unaffected embryos. To achieve these biopsy results, many IVF laboratories perform trophectoderm cell biopsies (TE), which is the development of embryos up to the blastocyst stage, which occurs 5-7 days after fertilization. Prior to trophectoderm cell biopsies (TE), biopsies were performed on polar bodies or cleavage embryos.

It is still open to debate the disadvantage discussed in the scientific literature that affects the technique's efficacy due to the presence of mosaic embryos and whether it should be paired with PGT for aneuploidy (PGT-A) for more concrete results.

4. STUDY OBJECTIVES

The **primary objective** of this retrospective observational single-center study is to describe the efficacy of PGT-M in a real-life setting. Efficacy will be evaluated in terms of live birth rate (LBR), simple and cumulative live birth rate (CLBR) per couple, and abortion rate (AR). Furthermore, investigators will consider how many cycles the participants need to undergo to achieve a viable blastocyst.

The **secondary objective** is to evaluate the incidence of aneuploidy in tested embryos, in order to understand the need for PGTA in addition to PGTM.

3.1. Endpoints

For the evaluation of the study objectives, all patients that underwent PGTM from 2016 to 2022 will be

included in the study.

The results obtained from the PGT-M will be calculated as:

Live birth rate (LBR): defined as the “the number of deliveries that resulted in at least one live birth, divided by the number of cycles.”

Embryology and Alpha Scientists in Reproductive Medicine. Electronic address [1]

Cumulative live birth (CLBR) per couple: defined as the “delivery of at least one live-born infant (>24 weeks of gestation) in the fresh or in the subsequent frozen-thawed cycles in relation to the number of oocytes retrieved per couple.” Polyzos, Drakopoulos [2]

Abortion rate (AR): is defined as the “spontaneous demise of a pregnancy before the foetus reaches viability. The term therefore includes all pregnancy losses (PLs) from the time of conception until 24 weeks of gestation.” Group, Vlasisavljevic [3]

Aneuploid embryo rate: “the most common genetic abnormality resulting in embryonic demise, pregnancy loss, and congenital birth defects. At the preimplantation stage, ~50% of the IVF-derived embryos have chromosomal abnormalities that are incompatible with implantation or normal fetal development.” Hindi E. Stohl [4]

4. STUDY POPULATION

4.1. Inclusion criteria

The study will include all fertile or infertile patients undergoing PGT analysis for monogenic diseases.

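### Entry depends on PGT-M having been performed, but the primary objective does not limit its per-couple efficacy claim to couples who reached biopsy and testing

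*Protocol*

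**What the plan says.** Every statement of the study population ties entry to the test having been done.

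- Section 4.1 (Inclusion criteria): "The study will include all fertile or infertile patients undergoing PGT analysis for monogenic diseases".
- Summary, planned number of patients: "All 76 patients who underwent PGTM testing in the Fertility Center", over 2016 to 2022.
- Summary, Study Procedures: "The study database includes all PGTM cycles performed between 2016-2022 at the Humanitas Fertility Center".
- The eligibility row of the Summary, section 3.1 (Endpoints) and section 4.3 (Recruitment) likewise describe patients who underwent PGT-M.

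The study flow-chart gives the procedure before PGT-M analysis as "Blastocysts trophectoderm biopsy". No section enrols couples by intention to have PGT-M, by start of stimulation or by oocyte retrieval.

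The Study Objectives section sets out to describe efficacy of PGT-M under real-life conditions through LBR, CLBR per couple and abortion rate. It adds that "investigators will consider how many cycles the participants need to undergo to achieve a viable blastocyst". Section 3.1 defines LBR as "the number of deliveries that resulted in at least one live birth, divided by the number of cycles" and CLBR "in relation to the number of oocytes retrieved per couple".

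**The concern.** Reaching biopsy happens after treatment has started. A couple with one or more retrievals intended for PGT-M but no blastocyst to biopsy has nothing to test and cannot be among the 76. Such a couple belongs in a real-life, per-couple account of the pathway and contributes no live birth to it. Leaving it out can only raise the rate.

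The same couples matter to the question of how many cycles are needed. Those who never obtain a blastocyst are the extreme of that distribution, and the entry rule removes them before anything is counted.

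The Background says of blastocyst-stage testing "which is already a method of selection as only good-quality embryos reach the blastocyst stage". That remark is about embryos. It shows how the selection could arise, not that any couple at this center was lost in this way.

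At stake is whether the reported rates describe couples who set out on PGT-M or only those who got as far as testing. The objective does not say which.

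**Working it through.** **Inputs.** From the Summary: 76 tested patients, taken here as 76 couples. Not in the documents: the number k of couples with retrievals intended for PGT-M who never reached biopsy, and any live birth count. Both are assumed below. The 76 is a census, not a calculated sample size, so there is no formula to reproduce.

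**1. CLBR per couple.** Read CLBR per couple as couples with at least one live birth, L, over couples. Assume never-biopsied couples add no live birth from this pathway.

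- Among tested couples: L/76.
- Among all couples who set out: L/(76 + k).
- Ratio: (76 + k)/76 = 1 + k/76, so the relative overstatement is k/76, whatever L is. One couple gives 1/76 = 1.3%.

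With an illustrative L = 38:

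| k | All couples | CLBR, tested only | CLBR, all | Relative overstatement |
|---|---|---|---|---|
| 0 | 76 | 50.0% | 50.0% | 0% |
| 1 | 77 | 50.0% | 38/77 = 49.4% | 1.3% |
| 4 | 80 | 50.0% | 38/80 = 47.5% | 5.3% |
| 8 | 84 | 50.0% | 38/84 = 45.2% | 10.5% |

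**2. LBR per cycle.** With D deliveries, C cycles among tested couples and m retrievals among never-biopsied couples, D/C replaces D/(C + m), a relative overstatement of m/C. Neither m nor a dependable C is given, so no figure follows.

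**3. Cycles needed.** A never-biopsied couple never achieves a viable blastocyst, whether viable means fit for biopsy or fit for transfer. It therefore has no value to add to the mean or median among couples who succeed, and leaving it out does not change that mean or median. What is lost is the count of couples who never succeed.

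**4. What the documents hint about k.** The flow-chart gives 567 embryos for analysis, so 567/76 = 7.46 per patient. Assume this yield is spread over 1, 2 or 3 cycles and is Poisson within a cycle. The chance z of no embryo to biopsy in a cycle is exp(-7.46) = 0.06%, exp(-3.73) = 2.4% or exp(-2.49) = 8.3%. If a couple stops after an unsuccessful cycle with assumed probability s, the share never biopsied is z·s/(1 - z(1 - s)). With s = 0.4 this is 0.02%, 1.0% or 3.5%. At 3.5%, k = 76 × 0.035/0.965, or about 2.8 couples; with s = 0.3 or 0.5 it would be about 2.1 or 3.4.

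This is only a rough guide. The figure 567 is called embryos in the flow-chart, children in section 6.1 and cycles in section 7.2. The average comes from couples who were already selected, and variation between couples would raise the chance of none.

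**The case against.** A retrospective series of tested patients is a legitimate descriptive target. Real-life can simply mean routine practice, and the protocol is open that its patients are those who had PGT-M. No passage shows that never-biopsied couples exist. If 567 is a count of embryos, the yield per patient suggests that few do. The registry may also not record intent, so the wider population might not be recoverable.

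Most of this stands, and it limits the size of the point. It does not remove it, because the objective states its claim without the restriction that the entry rule imposes.

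Several stronger readings are tempting but not supported.

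- A reader might infer that a percentage of couples achieving a viable blastocyst is misreported. The protocol plans no such percentage; it asks only how many cycles are needed.
- A reader might infer that the average number of cycles needed is biased downward. Among couples who succeed it is not, as step 3 shows.
- A reader might take PGT-M cycles to mean biopsied cycles only and conclude that LBR is badly inflated. If 70% to 90% of retrievals reached biopsy, dropping all others would inflate it by 1/0.9 - 1 = 11% to 1/0.7 - 1 = 43%. The protocol does not define cycle, and the cycles-needed question suggests that unsuccessful cycles are meant to count.
- A reader might see a contradiction with section 4.2, which states that no group is excluded. Read normally, it means no further exclusions after section 4.1.
- A reader might suppose that the rates will be used to counsel couples starting treatment. The documents do not say so.

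**Conclusion.** The point holds as a mismatch between population and claim. As written, couples whose retrievals never reached biopsy are outside the 76, while the objective speaks of real-life efficacy per couple without that limit. If such couples exist, CLBR per couple can only be overstated, by k/76 in relative terms. LBR per cycle is overstated as well, because their retrievals are missing from its denominator. The cycles-needed result omits couples who never succeed.

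The only dependable magnitude is about 1.3% relative per missing couple. It rests on one patient being one couple and on never-biopsied couples having no live birth from this pathway. The documents do not give k, and it may be small or zero.

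A reader might model a larger loss. Assuming that 80% of retrievals reach biopsy and 40% of couples stop after a failure gives 0.2 × 0.4/(1 - 0.2 × 0.6) = 9.1% never biopsied. Neither input comes from the documents, and the rough yield check points lower, so that figure should not be quoted as the size of the bias.

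**What to change.** Where the registry records PGT-M intent, redefine the population in section 4.1 as all couples with at least one retrieval intended for PGT-M in 2016-2022. Use those couples as the CLBR denominator and their retrievals as the LBR denominator. Report the number who never reached biopsy beside the number of cycles needed. Bring the Summary and sections 3.1 and 4.3 into line.

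If intent was not recorded, state in the Study Objectives section and in the Summary that all rates apply only to couples who reached biopsy and testing.

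The first option costs one further registry extraction and somewhat less favourable rates. The second costs one sentence and needs no new data.
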